## Goal: To determine if acute exposure to abnormal glucose levels induces mitochondrial fission and endothelial dysfunction through increased Drp1-Fis1 activity in humans.

Rationale: While DM often includes multiple metabolic abnormalities, the central phenotypical attribute of DM is abnormal systemic glycemic exposure. Hyperglycemia and hypoglycemia (occurring secondary to therapies), both acutely and chronically, are critical to both chronic and acute-on-chronic endothelial dysfunction in DM. Both exposures rapidly impair human vascular endothelial dysfunction through increased oxidative stress, inflammation, and a loss of NO bioavailability in both healthy non-DM subjects and patients with DM. 5-10 Hyperand hypoglycemia driven mitochondrial ROS production critically contribute to the development of endothelial dysfunction. However, the mechanisms behind the acute phenotypical change in the endothelium with acute hyperglycemic exposure remain poorly understood. Better understanding the mechanisms underlying the adverse impact of acute dysglycemia on the endothelium could lead to novel treatments to mitigate the burden and complications of CV events in patients both with and without DM.

Hyperglycemia also drives over-expression of Drp1 and Fis1 in the endothelium. Drp1 and Fis1 interact to drive mitochondrial fission leading to subsequent excessive mitochondrial superoxide production. Molecular suppression of Drp1 or Fis1 blocks hyperglycemia's adverse impact cultured endothelial cells. Our preliminary data show that Drp1 and Fis1 also control low glucose driven mitochondrial fission and excessive mitochondrial ROS production (Fig X or not shown). While there are multiple docking proteins for Drp1 on the outer mitochondrial membrane besides Fis1 (Mff, MiD49, MiD51), Fis1 is the preferred Drp1 docking protein in the setting of cellular stressors, including high glucose, in cell culture. These foundational data and our preliminary data strongly support our initial strategy of concentrating on Drp1 and Fis1.

In this study, we will test the hypothesis that acute in vivo exposure to hyperglycemia increases mitochondrial network fragmentation and mitochondrial ROS production in human arterial endothelial cells. Affirmative findings will critically establish that acute in vivo exposure to clinically relevant hyperglycemia levels in humans triggers mitochondrial fission and excess mitochondrial ROS production. Further. affirmative findings will establish that inhibition of mitochondrial fission proteins Fis1 and Drp1 reverses acute dysglycemiarelated endothelial dysfunction.

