unique outpatient visits over last year. The electronic health record is leveraged to identify potential subjects by HIPAA guidelines and MCW policies. .Potential subjects will undergo phenotyping that includes a detailed medical history, anthropomorphic measurements, blood pressure and heart rate measurements, and a blood draw for measurements that include fasting lipids, glucose, and glycosylated hemoglobin, creatinine, and liver function tests. Healthy, non-DM subjects who pass the screening as per the inclusion/exclusion criteria in Table 2 will be enrolled in the study protocol.

Following an overnight fast (12 hours), subjects will come in the morning to our Adult Translational Research Unit (A-TRU) which is part of the Clinical Translational Research Initiative of Southeast Wisconsin (8UL1TR000055). An antecubital intravenous line will be placed to facilitate blood glucose sampling during the hyperglycemic challenge. An antecubital intravenous catheter will be placed to facilitate obtaining endothelial cells from the vein by J-wire biopsy for of mitochondrial testing. The PI has published experience with the J-wire endothelial cell biopsy technique, and the technique has been extensively validated technique. An initial venous glucose sample will be taken from the antecubital vein and an initial J-wire biopsy of the radial artery endothelium will be performed through the radial arterial line. Subjects will then be asked to drink a standardized 75 g glucose drink created by the A-TRU nutritionist- a standard oral glucose challenge as used clinically. Blood glucose samples will be taken hourly after that until 2 hours post drink ingestion. At one and 2 hours post-ingestion, J-wire endothelial biopsies of the radial artery will be repeated. Three separate J wires will be passed into the radial artery for each measurement time point (0,1, and 2 hours).

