Data Analysis and Sample Sizes: The primary outcome for this sub-aim is the measurement of mitochondrial network complexity from before oral glucose administration to 1 hour afterward measurements. These will be compared by paired t-tests with log transformation for normality or non-parametric methods if needed. A secondary analysis using repeated measures ANOVA will also be performed using data from all 3 time points. Marginal/conditional residual diagnostics and influence diagnostics will be performed. If some of them are violated, log-transformation or non-parametric methods will be considered. Sample size calculations for mitochondrial network complexity measurements were derived from our observations of HUVECs described in our preliminary data section. The mean difference in network fragmentation in the preliminary data was 1.5±0.8 between normal glucose and high glucose exposure. Power analysis was performed for paired test and repeated measures ANOVA assuming 30% inflation in the number need to account for dropouts and failed J-wire captures. A mean difference between before oral glucose administration and 1 hour afterward measurements in network complexity was assumed to be 40% lower than our preliminary data in light of our less aggressive in vivo hyperglycemic exposure and the same standard deviation. Also, 4 hour afterward measurements were assumed to be back to the level of prior oral glucose administration. The correlation between time points was assumed to be 0.5. Then, we will need to recruit 15 subjects to have at least 90% power at  $\alpha$ =0.05 for paired t-test and repeated measures ANOVA. . Mitochondrial superoxide measurements are a secondary outcome whose results will be analyzed in the same manner as network fragmentation.

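### The stated conclusions go beyond the design: without a time or sham control a positive 1 h result cannot establish that hyperglycemia triggers fission, and nothing described tests Fis1/Drp1 inhibition

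*Combined protocol and SAP*

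**What the plan says.** The closing paragraph of the Goal section gives two conclusions to be drawn from positive results. The first is causal: "Affirmative findings will critically establish that acute in vivo exposure to clinically relevant hyperglycemia levels in humans triggers mitochondrial fission", together with excess mitochondrial ROS. The second concerns mechanism: "affirmative findings will establish that inhibition of mitochondrial fission proteins Fis1 and Drp1 reverses acute dysglycemiarelated endothelial dysfunction".

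The Protocol section describes one exposure, given to everyone after the baseline biopsy: "Subjects will then be asked to drink a standardized 75 g glucose drink created by the A-TRU nutritionist". It also says "Blood glucose samples will be taken hourly after that until 2 hours post drink ingestion" and "Three separate J wires will be passed into the radial artery for each measurement time point (0,1, and 2 hours". No water, sham, no-drink or time-control condition is described.

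Under Data Analysis and Sample Sizes, the primary outcome is network complexity before the drink and at 1 hour: "These will be compared by paired t-tests with log transformation for normality or non-parametric methods if needed". Then: "A secondary analysis using repeated measures ANOVA will also be performed using data from all 3 time points". For the other outcome: "Mitochondrial superoxide measurements are a secondary outcome whose results will be analyzed in the same manner as network fragmentation". No named analysis uses the glucose values. The same paragraph assumes, for power, that the outcome is back to its starting level 4 hours after the drink.

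**The concern.** Between 0 and 1 hour three things change together in every subject: glucose rises, an hour passes (with the fast extended up to the drink and the subject resting on the unit), and the artery has already had its baseline wires. The mean 1 h minus 0 h change is the sum of whatever these contribute, and without a comparator the data hold nothing that separates them. The repeated measures ANOVA responds to any pattern of change over the three times, so it does not separate them either. The same holds for superoxide.

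The reversal conclusion has a plainer problem. It describes the result of an intervention that does not appear in the procedures, on an endpoint that is not among the named outcomes.

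At stake is what may be said afterwards. If the conclusions stand as written, a time or sampling effect could be read as a causal glucose effect, and a treatment-relevant mechanism could be claimed that this study did not examine.

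**Working it through.** **1. The plan's own sample size.** Inputs from Data Analysis and Sample Sizes: preliminary difference 1.5 with SD 0.8, effect reduced by 40%, same SD, correlation 0.5, alpha 0.05, power at least 90%, 30% inflation. Sidedness is not stated; two-sided is assumed.

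- Effect: 1.5 × 0.6 = 0.9.
- SD of the paired difference: 0.8 × √(2 × (1 − 0.5)) = 0.8.
- Noncentrality for n pairs: (0.9 / 0.8) × √n. At n = 11 it is 3.73 on 10 df, power 91.8%; at n = 10 power is 88.5%. So 11 evaluable subjects are needed.
- Recruitment: 11 × 1.3 = 14.3, rounded up to 15. This matches the plan.

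**2. What a significant paired test can come from.** Write the mean change as G + A, where G is the glucose effect and A is everything else that changes between the two biopsies. The test addresses G + A = 0. Setting G = 0 and giving A an assumed size (the documents give none):

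| A (assumed) | P(significant), n = 11 | n = 15 |
|---|---|---|
| 0 | 5% | 5% |
| 0.2 | 11.7% | 14.7% |
| 0.3 | 20.3% | 27.3% |
| 0.45 | 39.3% | 52.7% |
| 0.6 | 61.2% | 77.1% |
| 0.9 | 91.8% | 98.1% |

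These are correct detections of a real change. They would be errors only if the change were then credited to glucose. The table is illustrative; the argument does not need A to be large, only that the design gives no estimate of it.

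**3. The reversal conclusion, set against the procedures.**

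| The conclusion needs | The document describes |
|---|---|
| A step that inhibits Fis1 or Drp1 | None |
| A measure of endothelial function | None among the named outcomes (network complexity, mitochondrial superoxide) |

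No value of either outcome could confirm or refute it.

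**4. The 4-hour assumption.** ANOVA noncentrality is n × Σ(mean at each time − overall mean)² / (0.8² × (1 − 0.5)), with denominator 0.32 and compound symmetry. With n = 11 the df are 2 and 20.

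- Full return at the last time, means 0, 0.9, 0: sum of squares 0.54, noncentrality 11 × 0.54 / 0.32 = 18.56, power 95.5%.
- Halfway back at 2 h, means 0, 0.9, 0.45: sum of squares 0.405, noncentrality 11 × 0.405 / 0.32 = 13.92, power 88.1%.

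The last biopsy is at 2 h, so the second pattern is possible, and it falls below the stated 90%. The primary paired test is unaffected.

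**5. Would the collected glucose values resolve the attribution?** Not for the mean change. I simulated 40,000 trials at n = 11 with a true glucose effect of 0.9 at 1 h, the same in all subjects. The model was a within-subject glucose slope with time as a 3-level factor, under five assumed sets of glucose means and spreads (for example 90/140/105 mg/dL with SDs 8/30/25). The slope was significant in about 5% of trials in every set, the same rate as under a pure artefact, because the time factor absorbs any effect common to all subjects. If the response instead follows each subject's own glucose exactly, with glucose measured without error, power ranges from 17% to 86% across those sets.

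**The case against.** The strongest reply is that no analysis here is wrong. A single-arm before-and-after challenge is a legitimate mechanistic design, the paired test holds its error rate for the question it asks, and the sample size reproduces. The sentences at issue are rationale, not a reporting rule. All of that stands, and it limits the point to the conclusions. The wording is still definite, and the paragraph introduces its hypothesis as that of this study.

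Supporting evidence can be cited: the plan refers to outside work on hyperglycemia and endothelial function, and its preliminary data compare normal with high glucose in HUVECs. This makes a glucose effect plausible but does not control the in vivo biopsy measurement. Superoxide is normalised to HUVECs stained at the same time, which deals with assay variation but not with in vivo time or wire effects. A return towards baseline at 2 h would argue against steady drift, but no such contrast is specified and an artefact that fades would look the same.

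The inhibition sentence may belong to a wider programme: Table 1 is titled for Aims 1 and 2, and the text calls this part a sub-aim. That is possible, and the remedy allows for it.

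A reader might also infer that leaving glucose out of the analysis is the error, and that adding it would cure the attribution problem. Step 5 of the working shows that it would not.

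**Conclusion.** The point holds as one about stated conclusions. A positive primary result would show a change after oral glucose under repeated sampling. It would not by itself establish that hyperglycemia triggers fission or ROS production, and no result could establish the Fis1/Drp1 reversal from what is described. The second part rests only on the text. The first rests on the absence of any described comparator; the percentages for artefacts rest on assumed shifts and show scale only.

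A reader might infer that the paired test is invalid, that 15 subjects is the wrong number, or that any observed change would be an artefact. The documents support none of these: the test is valid for mean change, 15 reproduces from 11 evaluable subjects, and nothing shows that a time or wire effect exists.

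The 4-hour assumption is a separate, smaller inconsistency. It affects only the ANOVA power, which is 95.5% or about 88% at 11 evaluable, depending on how far the outcome has returned by 2 h.

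**What to change.** Keep the design, the sample size and both tests.

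1. Reword the first conclusion in the Goal section so that a positive result is reported as a change after oral glucose, under repeated sampling, without a time control.
2. Remove the Fis1/Drp1 reversal conclusion, or tie it to a described inhibition step with an endothelial function outcome. If it belongs to another aim, say so.
3. Add a limitation: time or sampling effects on the mean 1 h minus 0 h change, for network complexity and for superoxide, cannot be excluded.
4. Reconcile the 4-hour power assumption with sampling at 0, 1 and 2 h, and restate the ANOVA power under the pattern assumed at 2 h.
5. Optional and exploratory only: a within-subject glucose slope with time as a 3-level factor, reported with its 95% CI. State that it cannot see a glucose effect common to all subjects, that it is imprecise at 11 evaluable, and that a null slope refutes nothing.

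The cost is wording and one restated power figure, with no extra visit, sample or subject. The downside is a more modest conclusion. None of this replaces a time control.

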unique outpatient visits over last year. The electronic health record is leveraged to identify potential subjects by HIPAA guidelines and MCW policies. .Potential subjects will undergo phenotyping that includes a detailed medical history, anthropomorphic measurements, blood pressure and heart rate measurements, and a blood draw for measurements that include fasting lipids, glucose, and glycosylated hemoglobin, creatinine, and liver function tests. Healthy, non-DM subjects who pass the screening as per the inclusion/exclusion criteria in Table 2 will be enrolled in the study protocol.

Following an overnight fast (12 hours), subjects will come in the morning to our Adult Translational Research Unit (A-TRU) which is part of the Clinical Translational Research Initiative of Southeast Wisconsin (8UL1TR000055). An antecubital intravenous line will be placed to facilitate blood glucose sampling during the hyperglycemic challenge. An antecubital intravenous catheter will be placed to facilitate obtaining endothelial cells from the vein by J-wire biopsy for of mitochondrial testing. The PI has published experience with the J-wire endothelial cell biopsy technique, and the technique has been extensively validated technique. An initial venous glucose sample will be taken from the antecubital vein and an initial J-wire biopsy of the radial artery endothelium will be performed through the radial arterial line. Subjects will then be asked to drink a standardized 75 g glucose drink created by the A-TRU nutritionist- a standard oral glucose challenge as used clinically. Blood glucose samples will be taken hourly after that until 2 hours post drink ingestion. At one and 2 hours post-ingestion, J-wire endothelial biopsies of the radial artery will be repeated. Three separate J wires will be passed into the radial artery for each measurement time point (0,1, and 2 hours).

Because of the prolonged fast, subjects may have a decrease in blood sugar to <70 during this study. To mitigate this phenomenon, subjects will be given 6 ounces of juice to drink at the 2-hour mark. If subjects report symptoms of hypoglycemia, which include but are not limited to feeling tremulous, headache, lightheadedness, feeling clammy or sweaty and nausea, the blood glucose level will be checked via a fingerstick. If the blood glucose level is < 70, they will be treated with juice and/or food. The fingerstick will also be repeated periodically to ensure adequate response to the intervention.

In non-DM subjects, the 75 g oral challenge induces a peak increase in systemic glucose at 1-hour postadministration at which time endothelial dysfunction is concomitantly detectable. While we could achieve a greater degree of hyperglycemia for a longer period using a hyperinsulinemic-hyperglycemic clamp procedure, the hyperinsulinemic-hyperglycemic clamp procedure fails to induce endothelial dysfunction, likely secondary to the pharmacological levels of insulin required for the protocol. Therefore, the oral glucose tolerance test is better suited for the purposes of this Sub-Aim.

A portion of the endothelial cells isolated from the J-wires will be used to measure mitochondrial network complexity prior hyperglycemic challenge, 1-hour post challenge, and 2 hours post challenge. We will visualize the mitochondrial networks in these cells using our previously reported and validated immunofluorescence method using cytochrome c antibodies to tag the mitochondria. Network fragmentation (high number=greater fragmentation and fission) will be quantified by network fragmentation count calculated with ImageJ (NIH, Bethesda) using a validated protocol adapted in collaboration with [name] from the University of Illinois-Chicago.

**SUB-STUDY:** The J-wire procedure proposed in this protocol is used to isolate endothelial cells and used to measure mitochondrial network complexity. In order to train (new) study staff on this procedure, as well as refine the best way to isolate these cells off the wires after they have been obtained from a subject approximately 20 subjects will be enrolled into a "sub-study" under this protocol. In this sub-study, subjects will sign informed consent one or two antecubital IV lines will be paced. The Research Fellow or PI will obtain endothelial cells by passing 1 to 3 J-Wires through the IV. No fasting is required of the subject and we will not need to collect any medical history on the subject. Subjects in this sub-study could enroll in the main study if desired, they would be consented again with the main study consent.

**PRELIMINARY DATA:** Our published work supports the feasibility of measuring mitochondrial network fragmentation in endothelial cells captured by J-wire biopsy.

Mitochondrial superoxide production using MitoSox™ (Life Technologies). Cells are re-suspended in PBS buffer and incubated for 30 minutes at 37°C with 5 µM of MitoSox™ (Invitrogen), a fluorescent probe specific for mitochondrial superoxide production. Cells are then immediately fixed with 2% paraformaldehyde and plated on

poly-lysine coated slides (Sigma, St. Louis) and allowed to settle. Following the addition of DAPI (4', 6'-diamidino-2-phenylindole hydrochloride) for nuclear identification to help discern endothelial cells from polymorphonuclear cells, fluorescence intensity of endothelial cells are measured by fluorescence microscopy (Nikon E55i). Images are analyzed using MetaMorph 6.1 (Universal Imaging). Fifteen to twenty cells are measured, and the average fluorescence intensity reported for each sample. All images are captured with the same exposure time. Values are reported ratios of subject fluorescence to that of human umbilical vein endothelial cells (HUVECs) stained simultaneously for

Blue- DAPI.

interexperimental normalization. **PRELIMINARY DATA:** We have successfully obtained vascular endothelial cells using the J-wire technique and measured mitochondrial superoxide production prior to and following lowering blood glucose levels for 1 hour, proving the feasibility of these measurements (**Figure. 2**).

Data Analysis and Sample Sizes: The primary outcome for this sub-aim is the measurement of mitochondrial network complexity from before oral glucose administration to 1 hour afterward measurements. These will be compared by paired t-tests with log transformation for normality or non-parametric methods if needed. A secondary analysis using repeated measures ANOVA will also be performed using data from all 3 time points. Marginal/conditional residual diagnostics and influence diagnostics will be performed. If some of them are violated, log-transformation or non-parametric methods will be considered. Sample size calculations for mitochondrial network complexity measurements were derived from our observations of HUVECs described in our preliminary data section. The mean difference in network fragmentation in the preliminary data was 1.5±0.8 between normal glucose and high glucose exposure. Power analysis was performed for paired test and repeated measures ANOVA assuming 30% inflation in the number need to account for dropouts and failed J-wire captures. A mean difference between before oral glucose administration and 1 hour afterward measurements in network complexity was assumed to be 40% lower than our preliminary data in light of our less aggressive in vivo hyperglycemic exposure and the same standard deviation. Also, 4 hour afterward measurements were assumed to be back to the level of prior oral glucose administration. The correlation between time points was assumed to be 0.5. Then, we will need to recruit 15 subjects to have at least 90% power at  $\alpha$ =0.05 for paired t-test and repeated measures ANOVA. . Mitochondrial superoxide measurements are a secondary outcome whose results will be analyzed in the same manner as network fragmentation.

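### Does a 4-hour power assumption undermine the sample size when measurements stop at 2 hours?

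*Combined protocol and SAP*

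**What the plan says.** The visit procedures in the Protocol section fix three biopsy times, one before the drink and two after it: "At one and 2 hours post-ingestion, J-wire endothelial biopsies of the radial artery will be repeated". Glucose sampling stops at the same point: "Blood glucose samples will be taken hourly after that until 2 hours post drink ingestion". The paragraph on the network assay agrees, using cells to "measure mitochondrial network complexity prior hyperglycemic challenge, 1-hour post challenge, and 2 hours post challenge".

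The Data Analysis and Sample Sizes paragraph makes the change from before glucose to 1 hour the primary outcome, tested by paired t-test. It then adds: "A secondary analysis using repeated measures ANOVA will also be performed using data from all 3 time points". The power statement covers both tests: "Power analysis was performed for paired test and repeated measures ANOVA assuming 30% inflation in the number need to account for dropouts" and failed wire captures. It takes a 1-hour difference 40% below the preliminary 1.5, with the same SD of 0.8. For the third mean it says: "Also, 4 hour afterward measurements were assumed to be back to the level of prior oral glucose administration". It continues: "The correlation between time points was assumed to be 0.5". The result is 15 recruits for at least 90% power at alpha 0.05 on both tests.

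**The concern.** The third mean enters the ANOVA noncentrality directly, and the plan attaches it to a time at which nothing is measured. Return to baseline by 4 hours does not imply return by 2 hours. Read literally, the ANOVA half of the power claim therefore rests on an input from a different schedule, and the input needed for the actual schedule is missing. If the 2-hour mean were partway back to baseline, ANOVA power could fall short of 90%. If that analysis had helped to set the sample size, 15 might be too few. A reader also cannot tell whether a 4-hour biopsy was dropped, mislabelled or still intended.

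**Working it through.** **Inputs from the Data Analysis and Sample Sizes paragraph.** Preliminary difference 1.5, SD 0.8, 40% reduction, correlation 0.5, alpha 0.05, 30% inflation.

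**Assumptions made here.** Two-sided testing (sidedness is not stated); inflation read as multiplication by 1.3; univariate F test with sphericity for the ANOVA (the plan names no specific test). The figure of 11 evaluable is back-calculated and does not appear in the plan.

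**Step 1: reproduce the 15.**
- Difference = 1.5 x (1 - 0.40) = 0.9.
- SD of the paired difference = 0.8 x sqrt(2 x (1 - 0.5)) = 0.8. It therefore makes no difference whether 0.8 is read as the SD at each time point or as the SD of the difference.
- Standardised effect = 0.9 / 0.8 = 1.125; noncentrality = 1.125 x sqrt(n).
- Noncentral t power: 88.5% at n = 10 and 91.8% at n = 11, so 11 evaluable are needed.
- 11 x 1.3 = 14.3, rounded up to 15. This matches the plan and uses no third time point. (Dividing by 0.7 instead gives 15.7, so 16.)

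**Step 2: ANOVA on the plan's own means.** Take the third mean as back at baseline: (0, 0.9, 0).
- Grand mean = 0.3; sum of squares = 0.09 + 0.36 + 0.09 = 0.54.
- lambda = n x 0.54 / (0.8² x (1 - 0.5)) = n x 0.54 / 0.32; at n = 11 this is 18.56, with 2 and 20 degrees of freedom.
- Power: 89.6% at n = 9, 93.1% at n = 10, 95.5% at n = 11.

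The ANOVA needs 10 evaluable and the t-test needs 11, so the t-test sets the sample size. A multivariate (Hotelling) test on the same means also passes at n = 11, with 90.7%.

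**Step 3: vary the unstated 2-hour mean.** The documents give no value, so the range from full recovery (0) to none (0.9) is an assumption. Univariate F test:

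| 2-hour mean above baseline | Sum of squares | Power, n = 11 | Power, n = 12 | Power, n = 15 |
|---|---|---|---|---|
| 0 | 0.540 | 95.5% | 97.1% | 99.3% |
| 0.225 | 0.439 | 90.6% | 93.3% | 97.7% |
| 0.45 | 0.405 | 88.1% | 91.2% | 96.7% |
| 0.675 | 0.439 | 90.6% | 93.3% | 97.7% |
| 0.9 | 0.540 | 95.5% | 97.1% | 99.3% |

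At n = 11, power is below 90% only between about 0.257 and 0.643, and the largest shortfall is 90 - 88.1 = 1.9 points. Simulation agrees: about 95.5% with a third mean of 0, and 88.0% to 88.2% with a third mean of 0.45.

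**The case for a change.** The best case for a change is that the plan makes its power claim for both tests, so both should be traceable to the design being run. Calling it a slip is an inference, because nothing in the documents says whether the hour is mislabelled or left over from another schedule. Nor is 88.1% a floor. At the same half-recovery mean, the univariate test has 84.1% power with 10 evaluable (a 30% loss from 15 leaves 10.5), and a multivariate test has 80.7% with 11. Keeping 90% for the univariate ANOVA at half recovery would take 12 evaluable, and 12 x 1.3 = 15.6, so 16 recruits.

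Part of this stands: the label does not fit the schedule, and the 2-hour mean is unstated. The rest depends on a partial-recovery mean that no document supplies. Even granting it, the univariate shortfall at 11 evaluable is under 2 points, for a secondary analysis, and it disappears at 12. The cost of keeping 90% in that case is one recruit. The lower figures also need either further losses or a test that the plan does not name.

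**Conclusion.** No change follows. The paragraph that mentions 4 hours also says that the ANOVA uses three time points, and the visit procedures and assay description agree on 0, 1 and 2 hours. The schedule itself is not in doubt, and an analyst would use the three measurements that exist. The natural reading is that the hour is a wrong label for the third scheduled point. On that reading the claim holds as stated: 91.8% for the paired t-test and 95.5% for the ANOVA at 11 evaluable.

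No stated figure is shown to be wrong. The 15 follows from the primary comparison alone, so neither the sample size nor the primary analysis depends on the third mean. Relabelling the hour, or writing down a 2-hour mean, would document a planning input for a secondary analysis and alter nothing that is done or concluded. This rests on a two-sided test, inflation by a factor of 1.3, and the plan's common correlation of 0.5. The mismatch is not evidence that the trial is underpowered.
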